Comparing Three Caries Prevention Products on Dentinal Hypersensitivity – A Pilot Study

NCT02136576

Protocol Version Date: 4/4/2017

I) Introduction

A) Aim/Hypothesis/Objective

The aim of this pilot research project is to compare the clinical effect on dentinal hypersensitivity of three products: Casein Phosphopeptide-Amorphous Calcium Phosphate (CPP-ACP) paste with fluoride, 5000 Sodium Fluoride (NaF) dentifrice containing Tri-Calcium Phosphate (TCP), and a dentifrice containing Potassium Nitrate.

The hypothesis of this study is that CPP-ACP with fluoride and 5000ppm NaF with TCP will exhibit a greater reduction in dentinal hypersensitivity compared to the control (dentifrice containing Potassium Nitrate).

The results of this pilot study will validate or negate the need for a larger clinical study that may provide generalizable results for using caries-prevention products with the additional benefit of minimizing dentinal hypersensitivity.

II) Background and Rationale

Dentinal hypersensitivity commonly occurs in patients with gingival recession, resulting from a reduced periodontium or in patients who have undergone non-surgical and surgical periodontal therapy.^{1,2} When the gingiva recede, the root surfaces of the teeth are exposed.³ In addition, after a non-surgical or surgical periodontal procedure, the cementum of the root surface is removed as a result of scaling and root planing. This leaves dentin exposed on the root surface with open dentinal tubules. In addition, dentin is less mineralized than enamel and has a greater susceptibility to and a faster progression of root caries and dentinal hypersensitivity.⁴ Root caries commonly occurs in patients who have undergone periodontal therapy and extensive root caries often results in the extraction of the tooth.⁵

Dental professionals often make a variety of recommendations to remedy dental hypersensitivity, including the application of fluoride varnishes, anti-hypersensitivity toothpaste, gingival grafting procedures and various restorative procedures, aiming to occlude the dentinal tubules or desensitize the pulpal nerve endings.^{6,7}

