This pilot study utilizes a single center, blinded, IRB-approved, randomized, prospective, paralleled group design to compare the reduction of dentinal hypersensitivity using CPP-ACP with fluoride or 5000ppm NaF with TCP to potassium nitrate (control).

B) Sample Size and Statistical Analysis

Sample Size

The primary analysis will be to compare the percent change in dentinal hypersensitivity between the 3 groups. We assume that the control group may exhibit a modest improvement in dentinal hypersensitivity (~5%) whereas the two test groups should demonstrate a more significant improvement (~30%). Assuming a common standard deviation of 25%, we will have 58% power to detect a difference between the 3 groups using one way analysis of variance, with 10 subjects per group, and setting alpha to 0.05 (nQuery Advisor, Version 7.0). Up to 13 subjects per group will be recruited, to allow for a more than 20% dropout rate.

The literature is varying on the amount of improvement possible with the products. Guidelines for sensitivity studies indicate that a main objective

should be to produce a clinically significant reduction in symptoms²⁰. With the use of VAS scores, a 30% decrease in VAS score has been shown to be clinically meaningful.^{18,19} For this study we anticipate a clinically meaningful decrease in sensitivity for the two test groups.

Statistical Analysis

Normality will be assessed using the Kolmogorov-Smirnov test. If the assumptions of normality hold, then means and standard deviations will be reported and the relationship between treatment arm and percent change in dentinal hypersensitivity will be tested using one-way ANOVA. If the assumptions of normality do not hold, then medians and interquartile ranges will be reported and relationships will be tested using the Kruskal-Wallis test. If the initial analyses are significant, then the *post hoc* pairwise comparisons will be made using either independent-sample t-tests or Mann-Whitney U-tests. When patients are lost to follow-up, their information will be excluded from the analyses.

All p-values less than 0.05 will be considered statistically significant. Analyses will be performed using SAS, Version 9.2 (SAS Institute, Cary, NC).

Randomization

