- Teeth with carious lesions, buccal vertical cracks in enamel, evidence of irreversible pulpitis (pain lasting more than five seconds after air stimulation)
- Pregnant/ lactating patients (Clinpro5000 has 5000ppm fluoride and there is a risk of ingesting the product)
- Patients with Milk Allergy (CPP-ACP is a dairy based product)
- Patients on Kidney Dialysis (due to the free calcium in CPP-ACP, dialysis patients should be on a diet with limited calcium)

3) Subject Withdrawal/Termination Criteria

- Subjects will be withdrawn from the study if they report the use of other dental hygiene products, including but not limited to: toothpaste, rinses, fluoride varnishes

- Subjects will be withdrawn from the study if they undergo any phase I periodontal procedures, including a prophylaxis or scaling and root planing
- Subjects would be withdrawn if they experience a negative side effect from any product used in the study.
- The tooth being studied is extracted, damaged from trauma or receives endodontic therapy.
- Subjects may participate in another research study at the same time, as long as it does not impact the results from this study.
- Subjects who do not comply with the study procedures, such as not returning for visits, not using product as documented in diary, may be withdrawn from the study.
- Subjects who become pregnant during the course of the study will be withdrawn. Subjects will be informed in the informed consent form to inform principal investigator or their designate if they become pregnant.
- Subjects who decide to stop participating in the study will be withdrawn.

The Principal Investigator will determine whether subjects (either withdrawn subjects or subjects completing the study) are in need of additional treatment and/or follow-up observation as a result of participation in this trial.

E) Assessment

1) Risk

This study poses minimal risk to subjects as these are products that are approved for use.

With Clinpro5000, although the patient will be instructed not to ingest the product, ingestion may result in GI discomfort, nausea, vomiting, diarrhea, cramping and fluorosis in children. Fluoride exposure should be monitored in pregnant and nursing women. Pregnant and lactating women and children will be excluded from this study.

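### Data from subjects lost to follow-up are discarded, and no planned analysis would show or reduce bias if that loss is selective and unequal between arms

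*Combined protocol and SAP*

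**What the plan says.** The handling of loss is one sentence in section III.B, Statistical Analysis: "When patients are lost to follow-up, their information will be excluded from the analyses". The rest of that section is a normality check, one-way ANOVA or Kruskal-Wallis on percent change, and pairwise follow-up tests. No analysis set of all randomised subjects, missing-data method, sensitivity analysis or tabulation of losses by arm appears anywhere.

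Dropout is otherwise addressed through numbers. Section III.B, Sample Size, says "we will have 58% power to detect a difference between the 3 groups using one way analysis of variance, with 10 subjects per group", and then "Up to 13 subjects per group will be recruited, to allow for a more than 20% dropout rate". Payment is staged by visit (III.H.5), and a poor recall rate is a ground for ending the study (III.M).

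Section III.D.3 lists the withdrawal reasons. Four of them are:
- Product side effects: "Subjects would be withdrawn if they experience a negative side effect from any product used in the study"
- Other products: "Subjects will be withdrawn from the study if they report the use of other dental hygiene products"
- Events on the study tooth: "The tooth being studied is extracted, damaged from trauma or receives endodontic therapy"
- Non-compliance: "Subjects who do not comply with the study procedures, such as not returning for visits, not using product as documented in diary" (here withdrawal is discretionary)

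Subjects may also leave by their own choice. The plan does not say how withdrawn subjects are analysed.

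Section III.F repeats the same sensitivity tests at weeks 2, 4 and 8. No visit is named as primary, and neither the air nor the water VAS is named as the primary stimulus.

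**The concern.** Randomisation makes the three groups comparable at entry. Excluding those who leave keeps them comparable only if leaving is unrelated to response, or is related to it in the same way in every arm. The sponsor allows for more than 20% dropout, and some of the listed withdrawal reasons could track the product or the response. The regimens also differ: Group II applies a second paste after brushing, while Groups I and III only brush.

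If loss were both response-related and unequal, a test product could look better or worse than it is, and nothing in the plan would show which. Section I.A gives the results a decision to inform: "The results of this pilot study will validate or negate the need for a larger clinical study". A shift in either direction could affect that decision.

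The rule also discards data that the trial pays to collect. Someone who attends at weeks 2 and 4 and misses week 8 has two post-baseline readings that, on the plain wording, go unused.

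**Working it through.** **1. The plan's own figures.** Inputs from III.B: mean improvements of 5, 30 and 30; SD 25; 10 per group; alpha 0.05.
- The grand mean is 65/3 = 21.67. The squared deviations sum to 277.8 + 69.4 + 69.4 = 416.7.
- The noncentrality is 10 × 416.7 / 25² = 6.67, with 2 and 27 df. Power is 58.1%, so the stated 58% reproduces.
- Dropout: 10 / (1 − 0.20) = 12.5, rounded up to 13. With 13 per group, 3/13 = 23.1% can be lost and 10 remain, which agrees with the stated allowance.
- Power is 71.6% if all 13 are kept, 52.8% with 9 left and 47.1% with 8 left.

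The arithmetic is sound. What it protects is the number of subjects.

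**2. Size of a selective-loss shift.** The documents give no loss mechanism, so the patterns below are assumptions. If 3 of 13 leave an arm and those lost average d SDs below their arm mean, the mean of the 10 who remain rises by (3/10) × 25 × d.
- *Mild* (loss correlated 0.3 with poor response): the lowest 3 of 13 normal values average 1.227 SDs below the mean, so d = 0.3 × 1.227 = 0.368 and the shift is 2.8 points.
- *Stronger* (3 lost at random from the 6 poorest responders): the lowest 6 of 13 average 0.811 SDs below the mean, so the shift is 6.1 points.

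Simulation with the plan's means (true difference 25, 3 of 13 lost in every arm, loss random in any arm not named):

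| Loss pattern | Mean difference | ANOVA power |
|---|---|---|
| Random everywhere | 25.0 | 58% |
| Stronger, every arm | 25.0 | 61% |
| Mild, control only | 22.2 | 49% |
| Mild, both test arms only | 27.7 | 69% |
| Stronger, control only | 18.9 | 37% |
| Stronger, both test arms only | 31.1 | 80% |

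With no true difference and selective loss in one arm, the ANOVA error rate goes from 5.0% to about 5.6% (mild) or 7.5% (stronger). Equal selective loss leaves the difference alone but lifts every arm's mean. In the stronger case 5 becomes about 11 and 30 about 36, which matters when arm means are read against the 30% that the protocol calls clinically meaningful.

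**3. Against sampling error.** The pairwise standard error is 25 × √(2/10) = 11.2. The 95% half-width is 2.05 × 11.2 = 22.9 (27 df). The shifts are 2.8/11.2 = 25% and 6.1/11.2 = 54% of one standard error.

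**4. What using the earlier readings recovers.** Assumptions: between-visit correlation 0.5 (range 0.3 to 0.7); selective loss in one test arm; one subject lost before Visit 2, one after week 2 and one after week 4, unless stated otherwise; a likelihood model without a baseline term.
- Loss driven by the last seen reading: the completer shift of 1.7 (1.1 to 2.3) falls to within 0.1 of zero.
- Loss driven by the unseen final score: 6.0 falls only to 4.8 (5.7 to 3.7 across the correlation range).
- All three lost before Visit 2: 6.1 stays 6.1.
- Random loss: effective n is about 10.5 per arm (10.1 to 10.9), and power about 60% (58 to 62%) instead of 58%.

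**5. The test statistic matters at this size.** Under no true effect, a three-visit model fitted by plain maximum likelihood with a chi-square test rejected in about 8 to 9% of simulated trials. A restricted-likelihood-type variance with an F test gave about 4.3 to 4.7%.

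**The case against.** The strongest reply is that the rule speaks only of subjects lost to follow-up, while nearly every reason for suspecting selective loss is a withdrawal under III.D.3. Only failure to return for visits links the two. That stands. A reader might infer that the plan prescribes a completers-only comparison with all withdrawn subjects dropped. That is a reasonable guess, but the documents do not say it.

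The magnitude also rests wholly on assumed loss patterns. Harm needs loss that is both response-related and unequal between arms, and even then it is at most about half a standard error. That stands too, and it limits the severity. A reader might go further and infer that the comparison is biased, or biased towards the test products. The documents give no loss mechanism and no loss by arm, so neither existence nor direction can be claimed. An extreme pattern, with the 3 poorest responders lost from both test arms and random loss in control, gives a spurious 9.2 points and about 19% false positives. Nothing in the documents supports assuming it.

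Finally, a repeated-measures model alone helps least where loss depends on unseen scores, and carelessly fitted it inflates the error rate by more than the stronger selective pattern does. Both are true. They shape the fix but do not defend the exclusion rule. Staged payment, the recall-rate rule and the pilot label do not fill the gap either: they bear on retention, numbers and consequence, not on how incomplete subjects are analysed.

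**Conclusion.** The point holds as a minor one that should be fixed because improvement is cheap. The wording gap is certain: collected readings are excluded under the plain text, and no planned analysis would show or reduce the effect of selective loss. The harm is only possible. Under the assumed patterns, with 23% loss per arm, unequal selective loss moves a between-arm difference by about 3 to 6 points against a standard error of 11.2. Random or equal selective loss moves it by nothing. The stated power and dropout arithmetic are correct, and the recruitment margin does what it claims, which is to preserve 58% power if the ceiling of 13 is reached.

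A reader might infer that keeping all the data would raise power to about 72%. That figure needs complete data on all 13 per arm. With losses spread over the visits the gain is about 2 points.

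**What to change.** Replace the exclusion sentence with: *Subjects are analysed in the group assigned, and all readings collected at weeks 2, 4 and 8 before loss or withdrawal are used.* Then:

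1. State that the rule covers both loss to follow-up and withdrawal under III.D.3.
2. Name one primary visit and one primary stimulus (air or water VAS).
3. Analyse percent change at that visit with a repeated-measures model adjusted for baseline VAS. Fit it by restricted maximum likelihood with a small-sample degrees-of-freedom correction (for example Kenward-Roger) and F tests. Do not use plain maximum likelihood with chi-square tests.
4. Keep the planned completer ANOVA or Kruskal-Wallis as a supporting analysis.
5. Add one simple sensitivity analysis for non-random loss. For example, assign no improvement to lost or withdrawn subjects, including those with endodontic therapy on the study tooth.
6. Report losses by arm and reason for all randomised subjects.

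The cost is revised wording, a little more analysis work and an IRB-approved amendment (III.L). No new visits, subjects or readings are needed. The model corrects only partly when loss depends on unseen scores, and not at all for loss before Visit 2, which is why item 5 is needed. The baseline adjustment was not part of the simulations above.

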Each subject will be randomized to a treatment arm using a randomization website (www.random.org). When subjects have multiple teeth eligible for the study, a separate randomization scheme (also from www.random.org) will be used to select that tooth. A printout of the randomization scheme will be used by the investigator distributing the products.

Blinding

Examiners collecting the sensitivity data will be blinded as to which group the subject is in. An investigator who did not examine the subject will distribute the product.

C) Products

Group	Product 1	Product 2
Group I (Control)	Sensodyne (Potassium Nitrate) manufactured by GalaxoSmithKline	N/A
Group II	Crest Cavity Protection manufactured by Procter and Gamble	MI Paste Plus (CPP-ACP with fluoride) manufactured by GC America
Group III	Clinpro 5000 (5000ppm NaF with TCP) manufactured by 3M ESPE	N/A

Sensodyne is FDA approved for decreasing tooth sensitivity. It is approved for use as it is being used this study.

Clinpro 5000 has been FDA approved for the prevention or reduction of dental caries. A reduction in dentinal hypersensitivity has been anecdotally documented in the literature.

MI Paste Plus is FDA approved for the reduction of dentinal hypersensitivity. It is approved for use as it is being used this study.

Crest Cavity Protection Toothpaste is FDA approved as an anticavity drug.

Oral-B 35 soft manual toothbrush is FDA approved and being used as approved for this study.

All products are being used according to manufacturer's instructions.

D) Subject Characteristics

1) Inclusion Criteria

- At least 18 years of age
- Tooth with exposed root surface and/or exposed dentin
- Tooth with a VAS score greater than or equal to 3
- No adjacent tooth/teeth with sensitivity (as defined as greater than 2 on the VAS)

2) Exclusion Criteria

- Participation in another dental study that may alter the results of this study.
- A medical condition that could interfere with reliable pain reporting (e.g., pain disorders)
- Any chronic medical condition that requires the regular use of pain or anti-inflammatory medications
- Used a desensitizing dentifrice within the preceding four weeks
- Have received an antihypersensitivity treatment (varnish or precipitating solution) of the identified tooth within the preceding four weeks
- Undergoing active orthodontic treatment.

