Air test: A 1 second blast of air from an air-water syringe that is set to 45psi at a distance of 10mm will be applied to the tooth. Adjacent teeth will be protected with fingers or cotton rolls. The subject will classify the extent of the sensitivity on the VAS. If the discomfort becomes intolerable, the stimulus will be immediately removed.

Water test: The patient will be given a 5-minute rest between tests. Disposable, plastic syringes filled with water will be kept in an ice water bath until use. Then, cold water will be applied to tooth using a plastic syringe with a plastic tip. Three drops of water will be placed on the tooth¹⁶. Adjacent teeth will be protected with fingers or cotton rolls. The subject will classify the extent of the sensitivity on the VAS. If the discomfort becomes intolerable, the stimulus will be immediately removed.

Schiff Test: The Schiff Sensitivity Scale²¹ will be utilized by the examiners to evaluate the response of the subjects to both the air and water test. This analog scale scores for the tooth as 0, 1, 2 or 3.

0-Tooth/Subject does not respond to stimulus.

1-Tooth/Subject responds to stimulus, but does not request discontinuation of stimulus.

2-Tooth/Subject responds to stimulus and requests discontinuation or moves from stimulus.

3-Tooth/Subject responds to stimulus, considers stimulus to be painful, and requests discontinuation of the stimulus

If the subject qualifies for the study, they will be entered into randomization.

Intraoral photographs of the study teeth will be taken. Photographs are for research purposes. Photographs will be taken at Visits 1 and 4. Additional photographs may be taken to document any adverse reactions.

After taking the data, the examiner will leave the operatory and another study team member will do the randomization. In this way the examiner will be blinded as to which group the subject is a part of.

Subject will be randomized to one of three groups:

Group I: Control

The control group will use Sensodyne toothpaste twice daily (2 minutes each time in the morning and the evening) during the duration of the study.

Group II:

Subjects will be instructed to brush twice daily (2 minutes each time in the morning and the evening) using Crest Cavity Protection toothpaste. They will be instructed to apply MI Paste Plus (CPP-ACP with fluoride) twice daily to the study teeth after brushing their teeth. MI Paste Plus will be applied to the study teeth with a finger.

Group III:

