A serious adverse event is one that results in death, or is life-threatening, or results in hospitalization or prolongation of existing hospitalization, or results in a persistent or significant disability/incapacitation, or results in a congenital anomaly/birth defect, or may jeopardize the subject's health and may require medical or surgical intervention to prevent one of the other outcomes listed above.

Serious adverse events will be recorded in source documents and on case report forms. Serious Adverse Events will be reported to the IRB within 15 business days.

Unanticipated Problems

An unanticipated problem is an incident, experience, or outcome that meets all of the following criteria: 1) The nature, severity, or frequency is unexpected for the subject population or research activities as

described in the current IRB approved protocol, supporting documents, and the ICF(s); 2) it is related or possibly related to participation in the research; 3) it suggests the research may place the subject or others at a greater risk of harm than was previously recognized.

Unanticipated problems will be recorded in source documents and on case report forms. Unanticipated problems will be reported to the IRB within 5 business days.

H) Subject Participation

1) Screening

The study co-investigators will conduct screening examinations to identify subjects who meet the inclusion / exclusion criteria for enrollment into the study.

2) Informed Consent

An investigator or study coordinator (who is GCP and CITI trained) will introduce the study. Patients will be asked to read the consent form and given ample opportunity to have their questions answered. An investigator will assess the patient's competency to provide consent by discussing the study with the patient and ensuring that they understand the study. Patients will certify their willingness to participate in the study by signing and dating the IRB approved informed consent document. The subject will be given a copy of the consent form.

If any new finding requires any change to the informed consent form, the subject will be reconsented.

Non-English speaking subjects will not be enrolled in the study because study staff at this time are not certified, prepared, or trained to translate or communicate in any language other than English. The study budget does not allow for the payment of translation services at this time.

3) Study Location

Tufts University School of Dental Medicine

4) Personnel

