Responsible for ongoing communication with the IRB – PI

Obtaining informed consent – PI, Co-Is, and study coordinator (who is GCP and CITI trained)

Maintaining study records – PI

Sensitivity testing and oral exam – PI and Co-Is

Product distribution and instructions, answering any questions that the subject has regarding the products. – Study coordinator (with instruction from PI/Co-I who has not treated subject).

Reviewing and collecting the patient's diary, handing out diaries - PI, study coordinator/team member

Intraoral photographs – PI, Co-Is

Gift card distribution – PI, study coordinator/team member

5) Payment for Participation

(a) Compensation

The subject will be given up to \$100 in gift cards. \$25 upon completion of visit 1, \$25 upon completion of visit 2, \$25 upon completion of visit 3, \$25 upon completion of visit 4.

(b) Transportation

No reimbursement will be given for transportation or parking

(c) Payment and Insurance

There will be no fees associated with the study procedures. Neither the subject, nor their insurance company, will be billed for any study procedures.

6) Study Results

If interested, a copy of the published paper will be mailed to interested study participants. A log will be kept of the participants who are interested in receiving study results.

7) Confidentiality

(i) To ensure confidentiality of subject information, each subject enrolled in the study will be assigned a unique alphanumeric code. Subjects' files will be kept in a secure, locked cabinet in a secure room (DHS-1418) when the files are not reviewed. The information will only be shared between the researchers. All HIPAA requirements will be followed. All electronic files will be kept on a password protected computer in a secure, locked office.

(a) Coding

(i) Each will be assigned a subject identification number. Alphanumeric identification numbers will be assigned sequentially. The full subject identification number will consist of the three letters from the subject's initials and their enrollment number. This will be accessible by study personnel only.

(b) Access / Data Safety Monitoring Board

Only study personnel will have access to data. Investigators will permit monitoring, audits, and regulatory inspections and will provide direct access to study related documentation.

10) Data Safety Monitoring Plan:

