Non-compliance with the clinical investigational plan, the Investigator

Agreement, applicable FDA regulations or conditions of approval imposed by the reviewing IRB

Withdrawal of IRB approval

In the event of study termination, the Principal Investigator will determine whether subjects are in need of additional treatment and/or follow-up observation as a result of participation in this trial.

N) Subject Recruitment/Advertising

Paper flyers will be posted throughout TUSDM, Tufts University School of Medicine and Tufts University School of Nutrition Science and Policy. Permission is not required for these posting locations. Flyers will remain posted until enrollment goals are met. Subjects will be recruited through responding to posted study advertisements. The same language from the approved flyers may be posted on the TUSDM website and screen in the lobby.

Investigators may also verbally inform clinic patients, faculty members who oversee students in the clinic, and post-graduate residents about the study.

Investigators may send messages to colleagues via axiUm or inform colleagues verbally, asking for their help in recruiting eligible subjects.

An email that alerts the TUSDM community to ongoing studies may include information on this study for recruiting purposes.

Advertisements/information regarding the study may be posted on Facebook and/or Craigslist.

All of the forms of recruitment will be submitted to the IRB for approval prior to use.

A screening interview/questionnaire or screening script will be used for recruitment. Screen failure data will be retained by PI. Screening ID number

and demographic information will be recorded. Identifiable information will not be recorded in the screening log.

O) References/Bibliography

- 3) West, NX. Dentine hypersensitivity: preventive and therapeutic approaches to treatment. *Periodontology 2000.* 2008; 48: 31-41.

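### No allocation concealment is described, and whichever role uses the randomization printout may also recruit, consent or screen later candidates

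*Combined protocol and SAP*

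**What the plan says.** The treatment sequence comes from a public randomization website (III.B, Randomization). The only sentence on how it is handled is: "A printout of the randomization scheme will be used by the investigator distributing the products".

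The protocol uses three labels for the person involved:

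- **Investigator.** III.B, Randomization, as quoted. The Blinding subsection adds that this investigator must not have examined that subject.
- **Study coordinator.** III.H.4 Personnel assigns product distribution as "Study coordinator (with instruction from PI/Co-I who has not treated subject".
- **Study team member.** III.F, Visit 1: "After taking the data, the examiner will leave the operatory and another study team member will do the randomization". The same section has a study team member explain the products before they are given out.

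Contact with candidates before randomization is shared among the same roles:

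- III.H.4: "Obtaining informed consent – PI, Co-Is, and study coordinator (who is GCP and CITI trained".
- III.H.2 Informed Consent: "An investigator or study coordinator (who is GCP and CITI trained) will introduce the study". An investigator then assesses competency "by discussing the study with the patient and ensuring that they understand the study".
- III.H.1 Screening gives the screening examinations to the co-investigators.
- III.N Subject Recruitment/Advertising: "Investigators may also verbally inform clinic patients, faculty members who oversee students in the clinic, and post-graduate residents about the study". It adds: "A screening interview/questionnaire or screening script will be used for recruitment". It does not say who conducts that interview.

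III.F places randomization after the subject has qualified and baseline scores have been taken.

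**The concern.** Randomization prevents selection only if nobody who influences entry can foresee the next assignment. Blinding the examiner after assignment is a separate safeguard. The plan provides the second and is silent on the first.

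If the printout shows future assignments, a person who has seen it and also recruits or consents could, even without intending to, affect who is approached or enrolled and when. That could unbalance the groups in ways the one-way comparison of percent change does not adjust for. It matters here because III.B plans on only 10 analysed subjects per group, and the Introduction says the result will decide whether a larger study is needed.

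**Working it through.** **Step 1: who may use the printout, and what else that role may do.**

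| If the user is | Source for that reading | Other permitted tasks |
|---|---|---|
| an investigator (PI or Co-I) | III.B, Randomization and Blinding | inform clinic patients (III.N), introduce the study (III.H.2), obtain consent (III.H.4); Co-Is also screen (III.H.1) |
| the study coordinator | III.H.4 | introduce the study (III.H.2), obtain consent (III.H.4) |
| another study team member | III.F, Visit 1 | not defined; III.H.4 names a team member only for diaries and gift cards |

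The first two readings put the printout and entry tasks in the same role. The third does not exclude it, because the PI, Co-Is and coordinator are also members of the team.

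**Step 2: do the separation rules prevent this?** The Blinding subsection and III.H.4 bar a person only in relation to a subject that person examined or treated. Someone who used the printout for one subject may approach, consent or screen the next. Of the eight task lines in III.H.4, none covers generating or holding the sequence. No section describes envelopes, central assignment, one-at-a-time release or an independent custodian.

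**Step 3: does the Visit 1 order close the gap?** For the current subject, qualification and baseline scores come first, the examiner leaves, and someone else randomizes. That protects the examiner's blinding for that subject. It does not hide later assignments from anyone who has seen a list.

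**Step 4: how many assignments could be known ahead?** Planned maximum: 3 × 13 = 39 (III.B).

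- Draw made per subject after baseline: 0 of 39.
- Full list printed: 39 of 39.

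For comparison, a simulation of 39 subjects gave the success rate of best guessing from past assignments without a list. It was about 33% under simple randomization, 61% with blocks of 3, 55% with blocks of 6 and 44% with one block of 39. The block figures assume the guesser knows the block size, which the protocol does not state. Reading a list gives 100%.

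**Step 5: the plan's own figures, then leverage per subject.** III.B assumes means of 5, 30 and 30, SD 25, 10 per group and alpha 0.05.

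- Grand mean = 65/3 = 21.67. Noncentrality = 10 × [(5 − 21.67)² + 2 × (30 − 21.67)²]/25² = 10 × 416.67/625 = 6.67. With 2 and 27 degrees of freedom, power is 58.1%, which reproduces the stated 58%.
- Dropout: 10/(1 − 0.20) = 12.5, rounded up to 13, as stated.

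Concealment changes neither figure. The same inputs give a sense of scale. Suppose one subject's percent change differs by 0.5 to 1 SD (an assumption), that is 12.5 to 25 points:

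- Shift in a group mean: 12.5/10 = 1.25 to 25/10 = 2.5 points.
- Share of the planned difference (30 − 5 = 25): 5% to 10%.
- Against the standard error of a two-group difference, 25 × √(2/10) = 11.2 points: 0.11 to 0.22 standard errors.

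This is leverage per subject, not an estimate of bias. How many subjects, if any, would be steered is unknown.

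**The case against.** A reader might infer that the coordinator works from the printout, obtains consent and therefore knows the next arm. The documents do not establish this. The Randomization subsection gives the printout to an investigator. One coherent reading is that a non-examining investigator holds it and instructs the coordinator, who hands over product without seeing it. This objection stands against naming the coordinator as the user. It does not remove the overlap, because investigators also recruit and consent, and Co-Is screen.

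A reader might also take the printout to be a list of future assignments. That is plausible but not stated. The protocol uses the same term, scheme, for choosing a study tooth, and III.F limits that choice to teeth tied on score, which are known only at the visit. Randomizing each subject after baseline also fits a draw made on the day, and then this route disappears. This objection stands, so the point must remain conditional.

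Other safeguards narrow the route:

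- Entry depends on a subject-rated VAS, and tooth choice follows a rule.
- If the coordinator holds the list, PI and Co-Is still decide eligibility.
- An investigator discusses the study with each patient.
- Screen-failure data are retained (III.N), so exclusions after screening leave a trace.

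These limit the scope for steering. They do not cover who is approached or when, and if an investigator holds the list, the investigator's role in eligibility and consent no longer acts as a check.

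**Conclusion.** The point holds in conditional form. The plan describes a printout, overlapping roles and per-subject separation, with no concealment. If the printout is an advance list, that arrangement can expose the next assignment to someone who approaches, consents or screens the next candidate. If assignments are drawn one at a time after baseline, it does not. Exposure therefore ranges from 0 to 39 of 39, and the documents do not say where in that range the trial lies.

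They do not support a claim that assignments were foreseeable, that selection occurred, or that the comparison is biased by any particular amount. The figure of 1.25 to 2.5 points per subject rests on an assumed 0.5 to 1 SD difference and gives scale only. The route is narrow. This is a change worth making in a small pilot, not a fatal flaw. The conflict among the three role labels needs correcting whatever the printout's format.

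**What to change.** 1. Replace the printout with sequentially numbered sealed opaque envelopes, or one-at-a-time release. Open each only after consent, eligibility, tooth selection and baseline scores are recorded. If draws are already made singly at that moment, say so.
2. State that whoever prepares the sequence or can see upcoming assignments does not recruit, consent, screen or examine later subjects.
3. Keep the master list sealed from those who do these tasks until enrollment closes. It can stay within the records that III.J.1 has the Investigator maintain, provided it is sealed.
4. Reconcile investigator (III.B), study team member (III.F, Visit 1) and study coordinator (III.H.4), so that one named role randomizes and distributes product.

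**Cost.** About 39 envelopes (3 × 13; screen failures use none) and wording changes, made by formal amendment with IRB approval under III.L. Sample size and power are unchanged. The downside is slightly less flexible role cover. For example, if the coordinator holds the list, the roles able to obtain consent fall from three to two (PI and Co-Is), who take over the coordinator's share of introductions and consent.
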